7.5 PK Population

All subjects who receive one dose of study drug and have at least one PK concentration result available post first dose (Debio 1562 or rituximab concentration, including value below limit of quantification). Reporting in the PK population will be done against the actual treatment received.

8 DATA HANDLING

8.1 Missing Data

Imputation rules for missing or partial dates are specified in [Appendix J](#). No other imputation of missing data will be implemented.

8.2 Coding

Adverse events, medical history, concomitant procedures, prior cancer related surgery and prior radiotherapy will be coded using the last available version of the medical dictionary for regulatory activities (MedDRA). Prior medications, prior cancer systemic therapy and concomitant medications will be coded using the last available world health organization drug dictionary (WHO-DD).

8.3 Handling of Values Below (or Above) a Threshold

For statistical and graphical summaries of the safety laboratory tests, values below or above the limit of detection (e.g. '< 3' or '>500') are substituted with the lower/upper limit of detection (e.g. '< 3' is substituted by 3, '> 500' is substituted by 500). In data listings, the values will be shown as collected, e.g. including the < or > sign.

8.4 Handling of Unscheduled Assessments or Retests

Unscheduled assessments will not be used in the summary statistics, but will be used in the derivation of endpoints that are not related to a specific timepoint. All values collected will be displayed in listings.

9.3 Multi-Centre Studies

Given the limited number of subjects expected per center, all centers will be pooled for the statistical analysis.

9.4 Timing of Analyses

The following analyses are planned to be performed:

- SRC/IDMC mandated analyses
- The primary analysis will be conducted after all enrolled patients have reached their 3rd on-treatment scheduled response assessment or have discontinued from treatment.
- The final analysis will be triggered one year after the last accrued patient's first dose date. In the exceptional case that after the final analysis any patients might continue to receive study treatment under the protocol. Any subsequent data generated from this patient(s) will be summarized in an addendum report to be issued after the last treatment and the safety follow up visit of the last patient.

Due to the COVID-19 epidemic and subsequent delays in data entry and cleaning, the primary analysis will in fact coincide with the final analysis.

10 STATISTICAL ANALYSIS METHODS

10.1 Disposition of Patients, Demographic and Baseline Data

10.1.1 Screen Failures and Eligibility Criteria

A subject is considered enrolled when informed consent is signed, eligibility criteria are met, and eligibility for Debio 1562 administration is confirmed.

Number and percentage of subjects screened, screened but not enrolled, and reasons for not being enrolled will be summarized.

Supportive by-subject listing for all subjects screened, along with whether the subject was a screen failure (as of <28 days prior to first dose of Debio 1562) and if yes, the reason for the screen failure.

Additionally, a second by-subject listing will be provided showing whether the subject continued to meet eligibility criteria on Cycle 1 Day 1 prior to dosing, and if not, which inclusion/exclusion criteria were violated.

10.1.2 Subject Disposition

Subject disposition will be displayed in a listing and summarized in a table by cohort and overall for the safety population.

The number and percentage of subjects completing treatment, treatment discontinuation from Debio 1562, treatment discontinuation from rituximab, study discontinuation, along with reasons for discontinuation, and treatment regimen switching from QW to Q3W due to the Covid-19 pandemic will be presented in a table and a listing by cohort and overall.

The primary reasons for treatment discontinuation from Debio 1562 and/or rituximab may include any of the following: progressive disease, adverse event, subject withdrew consent to treatment, subject withdrew consent to treatment and follow up, death, investigator decision (not related to an AE), study terminated by sponsor, significant protocol deviation, and other (reason will be specified in data listings).

The primary reason for study discontinuation may include any of the following: subject withdrew consent, lost to follow up, significant protocol deviation, sponsor decision, investigator decision, death, study completion, and other (reason will be specified in data listings).

10.1.3 Protocol Deviations

A deviation from the protocol is an unintended or unanticipated departure from the procedures or processes approved by the sponsor and the Institutional Review Board / Independent Ethics Committee and agreed to by the investigator. A major deviation occurs when there is non-adherence to the protocol by the subject or investigator that results in a risk to the subject, and/or the completeness, accuracy and reliability of the study data. All other deviations are minor. Descriptions of protocol deviations are listed in the Deviation Management Plan.

Protocol deviations will be summarized in a table by cohort and overall and displayed in a supporting listing.

10.1.4 Demographic and Baseline Characteristics

Baseline demographics will be summarized and listed by cohort and overall for all subjects in the safety population and will be repeated for all subjects in the efficacy evaluable population. Baseline demographic data to be evaluated will include age, sex, ethnicity, race, childbearing potential, height, weight, body mass index (body mass in kg divided by the square of the body height in meter) and body surface area. Age will be recorded on the electronic case report form (eCRF). Age will also be displayed in categories of 18-65 and > 65 years of age. No inferential statistics will be generated. Subject pregnancy test results will be included in a separate by-subject listing.

Moreover, baseline demographics will be summarized and listed [REDACTED]

[REDACTED].

10.1.5 Medical History

Medical history events will be coded using the medical dictionary for regulatory activities (MedDRA) per preferred term (PT) and system organ class (SOC). Summary of medical history will include number and percentage of subjects with a medical history condition overall, per SOC and per PT within each SOC. Listing will include condition/procedure, start and end dates and grade.

10.1.6 Disease Characteristics and Prior Therapy

10.1.6.1 Current Cancer Diagnosis

The current diagnosis will include the type of lymphoma, grade, [REDACTED]

and method of assessment for DLBCL, Ann Arbor staging system at initial diagnosis and current stage, longest diameter (LD_i, for listing only), shorter diameter perpendicular to LD_i (SD_i, for listing only), product of perpendicular diameters (PPD, for listing only), sum of the products of perpendicular diameters (SPD), results from cytogenetics/FISH/Molecular studies, [REDACTED], relapsed/refractory status, type of transformation if appropriate, extranodal disease status, Eastern cooperative oncology group (ECOG) performance status (PS). In addition, the International Prognostic Index (IPI) will be provided. The IPI is calculated² as the number of times the 5 following factors are met:

- Age above 60 years
- LDH above the upper limit of normal (ULN)
- Ann Arbor Stage III or IV
- ECOG PS ≥2
- Number of extranodal sites³ >1.

According to the revised IPI categorization (R-IPI), the prognosis is considered very good for IPI=0, good for IPI=1-2, and poor for IPI=3-5 (Sehn 2007).

All the aforementioned data will be summarized and listed by cohort and overall. Moreover, these data will also be summarized and listed [REDACTED] among the safety population, this will be repeated [REDACTED] among the efficacy evaluable population and repeated again [REDACTED] among the Per Protocol evaluable population.

10.1.6.2 Prior Cancer Systemic Treatments

Prior cancer systemic therapy (PCST), radiotherapy and cancer related surgeries will be presented in separate listings. Number and percentage of subjects per number of PCST line (reasons therapy was given, best response, reasons for discontinuing, number of cycles for first and last regimen, time from first dose to recurrence (relapse or progression), time from

² If one or more of the 5 factors are unknown, a range of possible IPI will be calculated for the subject. If the range is within one of the groups (IPI=1-2 or IPI=3-5), then the patient will be included in the grouped R-IPI analysis in [Table 3](#).

³ Number of extranodal sites is different from number of extranodal lesions if there are >1 extranodal lesions per disease site. For example, if there are 2 extranodal lesions but they are both in the liver, this will be considered as 1 extranodal site (The International Non-Hodgkin's Lymphoma Prognostic Factors Project, 1993). For the purpose of IPI calculation, the spleen is considered as an extranodal site (whereas it is considered nodal for the Ann Arbor classification). Bone marrow involvement should also be taken into account: if either the bone marrow biopsy or the bone marrow aspirate have lymphoma involvement, this should be considered as involvement in the organ "Bone". If liver is noted as having "diffuse liver involvement" at screening, that should also count as an organ.

last dose to recurrence), prior radiation (site, best response), and prior surgical procedure (residual disease) will be summarized. If the start and/or end date of PCST or the recurrence date is missing, it will be imputed (see Section 8.1). Moreover, these aforementioned data will also be summarized and listed [REDACTED] among the safety population and this will be repeated [REDACTED] among the efficacy evaluable population.

10.1.7 Prior and Concomitant Medications/Procedures

Medications/Procedures will be classified into two categories:

- Prior, defined as medications/procedures with start date before the first dose date;
- Concomitant, defined as medications/procedures administered during treatment period (from first dose date to the end of the period of safety observation).

All prior and concomitant medications will be coded using the World Health Organization Drug Dictionary (WHO-DD; version MAR2016 or higher). If the start and/or end date of concomitant medications is missing, it will be imputed (see Section 8.1).

Summary of prior and concomitant medication will include number and percentage of subjects with a concomitant medication overall, per ATC level 2 and per ATC level 4 within each ATC level 2. Separate supporting by-subject listings will be provided.

Additionally, the number and percentage who received a transplant will be tabulated under the prior medications summary table.

By-subject listing for concomitant procedures will be provided.

10.1.8 Eastern Cooperative Oncology Group Performance Status

Eastern cooperative oncology group (ECOG) performance status ([Appendix I](#)) will be assessed during screening and at other times specified in the schedule of events ([Appendix A](#), [Appendix B](#) and [Appendix C](#)). All measurements will be displayed in a data listing.

10.1.9 Bone Marrow Assessment

If applicable, a bone marrow biopsy or aspirate assessment will be performed within three months prior to the first dose. A repeat bone marrow biopsy or aspirate may be performed per investigator's discretion for subjects with bone marrow infiltration at baseline who have a CR. In order to better understand the effect of Debio 1562 on white blood cells, bone marrow biopsies or aspirates may also be requested for those subjects who experience grade 4 cytopenias. All measurements will be displayed in a data listing.

10.1.10 Tumor Biopsy

Subjects must provide a fresh or archived tumor biopsy sample at screening; archived tissue obtained within one year of the screening period is acceptable, provided that the subject's tumor(s) had not transformed during that time. Starting from protocol version 5, samples

obtained within 18 months of the screening period are acceptable. If transformation occurred one year (18 months for patients recruited according to protocol version 5 or later) prior to study treatment, the most recent tumor biopsy must be from after the latest transformation; otherwise a fresh biopsy must be collected. Tumor biopsy results from central laboratory [REDACTED] will be displayed in a data listing.

10.1.11 Transfusion Log

Subjects who received a transfusion during treatment will be presented in a listing including the date, blood product received, and indication.

10.2 Efficacy Analyses

All summaries will present data by cohort and overall for the efficacy evaluable population. The data summaries of Responses, OS, PFS, and DoR will also be presented by Cohorts and overall for the Efficacy evaluable population. Data summaries for OS and PFS analyses will also be presented for the All treated population.

Subject level data will be provided in listings.

10.2.1 Multiple Comparisons/Multiplicity

No formal comparison between cohorts will be performed. Therefore, adjustment for multiple comparisons will not be required.

Hypothesis testing will be done only for the primary efficacy endpoint. Therefore, adjustment for multiplicity will not be required.

10.2.2 Radiologic Tumor Assessment

Tumor response assessment is based on the Lugano classification of response assessment of Hodgkin and non-Hodgkin Lymphoma (Cheson, 2014, see Appendix H).

Radiographic tumor evaluation by computed tomography (CT) or positron-emission tomography (PET)-CT scan of chest, neck, abdomen, and pelvis will be performed within 28 days prior to first dose of study treatment. The anatomical regions to be assessed radiographically post baseline will be determined by individual subject's extent of disease. Repeat assessments will be performed every 6 weeks +/- 1 week, beginning at cycle 1, day 1 and will not shift as a result of delays in study treatment. The same radiographic assessment method used at screening should preferably be used at all subsequent evaluations.

The results from the tumor assessments will be listed for target, non-target, and new lesions including: lesion number, date, site, and method. For target lesions their measurements (LDi, SDi and PPD), sum of product of diameters (SPD), and FDG-PET Deauville score will be provided. Non-target lesions will be assessed and listed as present, not present, or unknown and whether worsened or not. An overall response will be determined by the investigators following the recommendations from the 2014 Lugano classification. If a new tumor is

identified, the date of biopsy, site, size, diagnosis of lymphoma per biopsy, grade, [REDACTED], [REDACTED], and method of assessment (if appropriate) will be listed. As per the 2014 Lugano classification, spleen and liver assessments will also be listed as appropriate.

Subject maximum percent change from baseline for the SPD (MCL, DLBCL, MZL, and FL) and the associated best overall response will be plotted (waterfall plot) for the efficacy evaluable population.

Subjects who have discontinued study treatment for reasons other than PD will be followed by radiographic assessment every 12 weeks (+/- 4 weeks), beginning from the time of the subject's last on-treatment tumor assessment, until documentation of PD, or beginning subsequent anti-cancer therapy. The date of attempted contact, PD status, new anti-cancer therapy status, regimen, and dates will be listed.

10.2.3 Primary Efficacy Analysis

The BOR is the best response recorded from the start of the treatment until disease progression or initiation of new anti-cancer therapy or end of the study period, whichever occurs first. Additionally, best response will be evaluated from first dose date up to first on-treatment scheduled assessment, up to second on treatment scheduled assessment, up to third on-treatment scheduled assessment, and up to End of the treatment period, i.e. up to the date of last cycle day 1 + 21 days..

Response assessment will be determined by the investigator for each subject as:

- Complete (metabolic) response (CMR/CR)
- Partial (metabolic) response (PMR/PR)
- No metabolic response or stable disease (NMR/SD)
- Progressive (metabolic) disease (PMD/PD)
- Not evaluated (NE)
- Not done.

The following rules will be applied to define period:

- From first dose date up to first on-treatment scheduled assessment:
 - o From first dose date up to 6 weeks + 7 days from first dose date
- From first dose date up to second on-treatment scheduled assessment:
 - o From first dose date up to 6 weeks + 7 days from first on-treatment scheduled scan if first on-treatment scheduled scan is performed
 - o From first dose date up to 12 weeks + 14 days from first dose date if first on-treatment scheduled scan is not performed
- From first dose date up to third on-treatment scheduled assessment:
 - o From first dose date up to 6 weeks + 7 days from second on-treatment scheduled scan if second on-treatment scheduled scan is performed
 - o From first dose date up to 12 weeks + 14 days from first on-treatment scheduled scan if second on-treatment scheduled scan is not performed but first on-treatment scheduled scan is performed
 - o From first dose date up to 18 weeks + 21 days from first dose date if first and second on-treatment scheduled scan are not performed.

The ORR is defined as the proportion of subjects with a BOR of PR or CR. The BOR and ORR will be tabulated along with percentages.

Ninety-five and eighty percent two-sided exact confidence intervals (CIs) will be constructed using the Clopper-Pearson method (Clopper, 1934). For the analyses carried out by cohort, the one-sided exact binomial distribution will also be used to test the hypotheses that the ORR is below or on 40% and above or on 60%, respectively.

The following sensitivity analysis will be performed:

- An additional analysis will be done by censoring the Cohort B subjects who have switched to Q3W regimen at their last assessment date while they were still in QW regimen

10.2.4 Secondary Efficacy Analyses

Progression free survival (PFS), OS, and DoR will be analyzed using the Kaplan-Meier method in both summary tables and figures. The number and percentage of subjects censored and those with events will be summarized. Additionally, the median, 25th and 75th percentile estimates and 95% CI (where calculable based on Brookmeyer and Crowley 1982), and minimum and maximum in months will be presented. The PFS rate, DoR rate and OS rate, calculated at 3, 6, 9, 12, 15, 18, 21, 24, and last point of observation months will be presented along with 95% CI (using the log-log transformation) based on Kaplan-Meier product limit estimates. The denominator for event/censored rates will be the number of subjects within each cohort and total. Time to response will be analyzed using descriptive statistics only.

10.2.4.1 Progression Free Survival

PFS is defined as the time (in months) between the date of the first Debio 1562 dose until the earliest of either first occurrence of PD (radiologic or clinical) or death. It is calculated as:

$$(date\ of\ first\ PD/death - date\ of\ first\ Debio\ 1562\ dose + 1) / 30.4375.$$

The following censoring rules will be applied:

1. Subjects who do not experience death or PD, nor initiate a new systemic therapy will be right-censored at the date of their last adequate tumor assessment (i.e. a tumor assessment not showing NE);
2. Subjects having initiated a new systemic therapy before experiencing death or PD will be right-censored at the date of their last adequate tumor assessment prior to initiation of a new systemic therapy;
3. Subjects who experienced death or PD after two or more consecutive missing or inadequate tumor assessments (i.e. $2*6*7 + 2*7 = 98$ days, based on assessments every 6 +/- 1 week) while assessments are done every 6 +/- 1 week will be right-censored at their latest adequate assessment before death or PD;

4. Subjects who experienced death or PD after one or more consecutive missing or inadequate tumor assessments (i.e. $12*7 + 4*7 = 112$ days, based on assessments every 12 +/- 4 week) while assessments are done every 12 +/- 4 week will be right-censored at their latest adequate assessment before death or PD;
5. Subjects without a baseline or post-baseline assessment will be right-censored at the date of first administration of the Debio 1562 unless the subject died within 190 days from the first dose date ($5*(21+3)+21+7+42 = 190$ days, considered as an event at the date of death).

If multiple event and censoring conditions are met for the same subject, then the condition with the earliest date will be selected.

When an analysis cutoff date is implemented, only data occurring on or prior to the cutoff date will be used for analysis and subjects will be censored at the latest adequate assessment prior to cutoff date.

The following sensitivity analyses will be performed:

1. An additional sensitivity analysis for progression-free survival consists of ignoring the 3rd and 4th censoring rules.
2. For progression-free survival, subjects who do not experience disease progression or death or who initiate anti-cancer therapy other than for a transplant or CAR-T will be right-censored at the date of their last adequate tumor assessment using the same rules as above. Hence, data collected after a transplant therapy or CAR-T until PD, death or last adequate tumor assessment - whichever occurs first will be included in the PFS derivation.
3. An additional analysis will be done by censoring the Cohort B subjects who have switched to Q3W regimen at their last assessment date while they were still in QW regimen
4. An additional analysis will be done by censoring the subjects who died due to Covid-19 at their death date, if they haven't progressed yet.

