### **8.14. Radiologic Imaging and Tumor Response Assessment**

Tumor response assessment will be based on the 5-point scale per the Lugano classification of response assessments of Hodgkin and NHL ([Cheson 2014](#)).

Radiographic tumor evaluation by computed tomography (CT) or positron-emission tomography (PET)-CT scan of chest, neck, abdomen, and pelvis will be performed within 28 days prior to first dose of study treatment. The anatomical regions to be assessed radiographically post baseline will be determined individually by extent of disease. Though less preferred, a MRI is acceptable. Patients with FDG-avid disease will be followed by [ $^{18}\text{F}$ ]-FDG-PET scan. Repeat assessments will be performed every 6 weeks  $\pm$  1 week, beginning at Cycle 1, Day 1 and will not shift as a result of delays in study treatment.

Whenever possible, the same radiographic scan assessment used at screening (e.g., PET-CT) should be used at all subsequent radiographic evaluations.

**Response Follow-up:** Patients who have discontinued study treatment for reasons other than PD will be followed by radiographic assessment every 12 weeks ( $\pm$  4 weeks), beginning from the time of the patient's last on-study tumor assessment, until documentation of PD, or beginning subsequent anti-cancer therapy or death.

For patients who are exceptionally granted continued study treatment after completion of 6 cycles, repeat radiographic tumor response assessments can be performed as per local institutional care practice. Ideally, repeat assessments should continue at 6-week ( $\pm$  1 week) intervals and should not be longer than 12-weeks ( $\pm$  4 weeks). Periodic tumor assessment will be conducted using the same imaging modality of prior cycles of treatment until PD, start of any new anti-cancer therapy, or death.

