10.2.4.2 Duration of Response

Duration of Response is defined as the time between the earliest date of CR or PR response and the date of the first occurrence of PD or death and calculated as:

$(date\ of\ first\ PD/death - date\ of\ first\ CR/PR + 1) / 30.4375.$

Censoring rules for PFS will be applied to DoR. The DoR will be estimated for all evaluable subjects who achieve an objective response of PR or CR.

The sensitivity analyses for PFS will also be reproduced for DoR.

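### PFS and DoR censoring rule 4 (SAP 10.2.4.1) can censor PD or death 113 to 140 days after an in-window follow-up scan although no scan was missed

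*SAP*

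**What the plan says.** SAP 10.2.4.1 has two censoring rules for events after missed scans. Rule 3 covers the 6-weekly phase, requires two or more missed scans, and sets the limit at "2*6*7 + 2*7 = 98$ days, based on assessments every 6 +/- 1 week". Rule 4 covers the 12-weekly follow-up phase, requires one or more missed scans, and sets the limit at "12*7 + 4*7 = 112$ days, based on assessments every 12 +/- 4 week) while assessments are done every 12 +/- 4 week". Under both rules the patient "will be right-censored at their latest adequate assessment before death or PD".

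Protocol 8.14 has patients who stop treatment without PD "followed by radiographic assessment every 12 weeks ( $\pm$ 4 weeks), beginning from the time of the patient's last on-study tumor assessment". SAP 10.2.2 has them "followed by radiographic assessment every 12 weeks (+/- 4 weeks), beginning from the time of the subject's last on-treatment tumor assessment". Footnotes to the schedules of events in Protocol Appendices A to C repeat the single starting point.

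SAP 10.2.4.2 extends the rules: "Censoring rules for PFS will be applied to DoR". Sensitivity analysis 1 in SAP 10.2.4.1 ignores rules 3 and 4 for PFS, and SAP 10.2.4.2 repeats the PFS sensitivity analyses for DoR.

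**The concern.** Rule 4 states a condition in words (a follow-up scan is missing or inadequate) and then replaces it by a day count. The count should not be met by a patient who has missed nothing. It adds one ±4-week window to one 12-week interval. If every follow-up visit is timed from a single date, both scans that bound an interval can move: the earlier forward and the later back. A compliant interval can then exceed the limit.

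Where that happens, an observed progression or death becomes a censoring at an earlier scan in the main PFS and DoR analyses. The patients exposed left treatment without PD, and they inform the later part of the Kaplan-Meier curves, for which SAP 10.2.4 reports rates out to 24 months. Removing events there tends to raise the estimates.

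**Working it through.** **Inputs.** Follow-up interval 84 days and window ±28 days, from one anchor (Protocol 8.14, SAP 10.2.2). On-treatment interval 42 days and window ±7 days (SAP 10.2.2). Limits of 98 and 112 days (SAP 10.2.4.1). The SAP does not say whether a gap equal to the limit counts; I take the cut as more than 112 days.

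**The plan's own figures reproduce.** 2×6×7 + 2×7 = 98, and 12×7 + 4×7 = 112.

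**Range of gaps between adequate scans.** Let I be the interval, W the window, m the number of scans missed in between, and k = m + 1. With a fixed anchor the gap runs from kI − 2W to kI + 2W. With a rolling schedule, where each window restarts at the previous scan, it runs from k(I − W) to k(I + W).

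| Phase | Missed | Fixed anchor (days) | Rolling (days) | SAP limit |
|---|---|---|---|---|
| 6-weekly | 1 | 70–98 | 70–98 | 98 |
| 6-weekly | 2 | 112–140 | 105–147 | 98 |
| 12-weekly | 0 | 28–140 | 56–112 | 112 |
| 12-weekly | 1 | 112–224 | 112–224 | 112 |

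Rule 3's limit separates one missed scan from two on either reading. Rule 4's limit separates none from one only if windows roll. With a fixed anchor, compliant gaps of 113 to 140 days are read as a missed scan.

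**Example.** The first follow-up scan is at day 84 − 28 = 56 (week 8) and the second at day 168 + 28 = 196 (week 28). Both are in window, and the gap is 196 − 56 = 140 days. PD at the second scan is censored back to week 8. A patient scanned at week 8 who dies at week 25 is (25 − 8)×7 = 119 days from the last scan. That death is also censored, although the next window stays open to week 28.

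**Which events are exposed.** A follow-up scan d days from its nominal date leaves (84 + 28) − d = 112 − d days until the next window closes. That exceeds 112 only when d is negative, so only patients whose previous follow-up scan was early are exposed. The first follow-up scan is due at most 84 + 28 = 112 days after the anchor, which is itself an actual scan, so an in-window first scan cannot breach the limit.

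**Share of compliant consecutive follow-up gaps above 112 days.** The documents do not give the distribution of scan timing; these are assumptions.
- Independent and uniform over ±28 days: 28² / (2×56²) = 784 / 6272 = 12.5%.
- Normal around the nominal date, truncated to the window (simulated): 0.2% with SD 7 days, 2.1% with SD 10, 5.5% with SD 14.
- All scans within ±14 days: the largest gap is 84 + 14 + 14 = 112, so none.

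These are shares of gaps, not of patients or events.

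**Would 140 days work?** With a fixed anchor, one missed scan can leave a gap as short as 112 days, so gaps of 112 to 140 days arise with and without a missed scan. In particular, a patient who misses the first follow-up scan (due by day 112) and progresses on days 113 to 140 would escape a 140-day limit.

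**The case against.** The strongest reply is that 112 is deliberate and correct because follow-up windows roll. Both documents say where the follow-up series begins but do not spell out each later visit. The explicit statement that the calendar does not shift is made for on-treatment scans only. The best-response periods in SAP 10.2.3 count from the previous scan where there is one and allow one window per interval. For treatment extended beyond Cycle 6, Protocol 8.14 puts the ±4-week tolerance on the interval itself. Rule 3 fits this pattern too, since 98 = 2×(42 + 7).

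Much of this stands. A reader might infer that 112 is a calculation error, or that rule 3 proves an allowance for a window at both ends was intended. Neither follows: 112 reproduces exactly and is right for rolling windows, and 98 fits either reading. What does not stand is that the documents adopt rolling windows for this follow-up. SAP 10.2.3 concerns on-treatment periods, and the extended-treatment sentence concerns patients still being treated. For patients off treatment, both documents name one starting scan and nowhere restart the window; the SAP's wording ties it to the last scan on treatment.

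It is also fair to say that the consequences are limited. PFS and DoR are secondary, SAP 10.2.1 confines hypothesis testing to the primary efficacy endpoint, and sensitivity analysis 1 would expose any effect. But that analysis also stops censoring after scans that really were missed, so it bounds the problem without giving a corrected main estimate.

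**Conclusion.** On the plain wording of the follow-up schedule, rule 4's day count does not match its stated condition. PD or death 113 to 140 days after an in-window follow-up scan can be censored with no scan missed, in the main PFS and DoR analyses. This rests on the single-anchor reading; if windows roll, 112 days is right and the SAP need only say so.

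A reader might infer that compliant patients are routinely censored or that the curves are materially inflated. The documents do not support that. Only events after an early follow-up scan are exposed, in-window first follow-up scans are not, and ORR is untouched. The share of compliant gaps runs from none to 12.5% depending on assumed timing, and the documents give no basis for a count of affected patients. It is a modest defect in secondary analyses, worth correcting because the correction is cheap.

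**What to change.** Replace the 112-day count in rule 4 with a closed-window condition: censor at the latest adequate scan only if, between that scan and the PD or death, a scheduled follow-up window (last on-study scan + 12k weeks ± 4 weeks, k = 1, 2, 3, …) closed without an adequate scan. State in the SAP that this anchor is the last on-treatment scan and that windows do not restart, and apply the same rule to DoR. Do not substitute a flat 140 days, for the reason shown in the working. If the sponsor did intend rolling windows, keep 112 days, say so, and state whether the cut is above or at 112.

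The cost is slightly more programming, since windows must be derived for each patient. PFS and DoR may come out slightly less favourable. Sensitivity analysis 1 can stay as it is.
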